#### V. Post-treatment Assessments at 3-Months and at 9-Months (Six-month follow-up)

At the conclusion of the 3-month intervention (post-treatment), or at the time a participant may drop out of the study (or in the rare instance of requiring additional or different anxiolytic treatment outside of our protocol), patients will complete the same clinical, biomarker, and psychometric test battery that they completed at baseline. At the 6-month follow-up, we will assess anxiety, patients' exercise habits, any psychiatric treatment, psychopharmacologic medications, aerobic fitness using a 6-minute walk test, and cardiac status, including revascularization procedures and CHD events. This will be a naturalistic follow-up that we have used in previous trials,[157, 158] which will allow us to determine patients' anxiety status 6 months after the conclusion of study-related treatment, along with changes in health habits and measures of quality of life. Figure 2 presents an expanded view of the assessment schedule and design of the study. For clinical events, we carefully will document cardiac-related hospitalizations and

emergency room visits, revascularizations, and any deaths for up to 4 years post-treatment.

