## **12. Data Management and Statistical Considerations**

**Data Analytic Approach.** The basic analytic strategy is a linear model carried out in the MPlus modeling software,[164] with treatment group contrasts as factors, and ethnicity, age, gender, and pre-treatment measure of the outcome variable as the adjustment covariables. The intent-to-treat principle (ITT) will be followed in all models, using full information maximum likelihood available in MPlus to manage missing data. For the case of the primary outcome, HADS-A, the model will include post-treatment HADS-A score as the response, with the predictors including two planned contrast variables representing 1) the two active treatments (exercise and escitalopram) vs. placebo and 2) exercise vs. escitalopram, with ethnicity, gender, age, and pre-treatment level of the HADS-A as the adjustment covariables. The contrast tests among treatment groups will be examined directly, i.e., no omnibus or “gateway” test will be required before interpreting them. In support of the HADS-A outcome, we also will compare the pattern of weekly changes in the STAI scores over time using a repeated measures model with Proc Mixed in SAS (SAS Institute, Cary, NC). The primary biomarker outcome, HRV, will be evaluated similarly. It is possible that a small number of participants may require off-protocol psychotropic medication during the course of the trial. These participants will be included in the ITT analysis and will not be replaced. We also will perform a sensitivity analysis with change in medication included as an adjustment variable in the statistical model. Finally, we will compare the treatments on the number of clinical events using a generalized linear model with the appropriate distributional form (e.g., negative binomial), using the same contrasts and covariates as in the linear model described above.

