In addition to treatment effects, we also will test the hypothesis that pre- to post-treatment change in HADS-A scores will mediate the improvements in intermediate CHD biomarkers. M-Plus allows a direct, formal test of this hypothesis via path analysis modeling. For example, a model will be specified so that both active treatment groups will be contrasted against the placebo arm, with a variable representing the change in anxiety intervening between the treatment contrast variables and post-treatment HRV (with the covariates, pre-treatment HRV, age, ethnicity, and gender). Mediation is tested by examining the product of the two component path coefficients (treatment → mediator → outcome) and its standard error, which yields the point estimate of the mediated effect along with the statistical significance of treatment on post-treatment biomarker (e.g., HRV) via change in HADS-A.[165] We also will explore possible treatment-specific mediators (e.g., change in VO2 mediating change in HRV for the Exercise group). In addition to the above tests, we will examine the impact of dropout on the estimates

of treatment effects using mixture modeling available in MPlus. Specifically, we will examine the primary outcomes using Rubin's Complier-Average Causal Effect Estimation (CACE) model,[166] which estimates the effect of treatment for all participants who adhere to the protocol irrespective of treatment group assignment. We will explore possible moderators of the treatment effect using interaction terms. Specifically, we will examine the possible moderating effects of gender, race, patient expectations, and initial severity of anxiety (e.g., DSM-5 diagnosis for an anxiety disorder); if sufficient numbers, we also plan to explore individual diagnoses by adding treatment interaction terms for these variables simultaneously with the primary model, and using a pooled test of the terms to determine whether the individual terms should be interpreted. Participants who voluntarily drop out of treatment or who are unable to complete our protocol will not be replaced but will undergo follow-up assessment.

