**Power Analysis.** Our study is powered with a focus on the primary hypothesis test: the treatment effect on anxiety as measured by HADS-A scores. We estimated power and sample size under the following assumptions: an alpha of .05, a linear model with age, gender, ethnicity, and baseline HADS-A score as covariates, a conservative estimate of the R-squared of .20 for the full model predicting post-treatment HADS-A, a 15% attrition rate, and two planned contrasts: active treatment vs. placebo and exercise vs. escitalopram. The comparison of primary interest will be active treatments vs. placebo. We estimate that a sample size of 150 (127 after attrition) will yield .80 power to detect at least a .45 SD difference between the active treatments and Placebo. In the general linear model, the exercise vs. escitalopram test will be only slightly less powered in being able to detect a .50 SD difference. In response to a previous reviewer comment, we believe that achieving this effect size is feasible. For example, in individuals with high anxiety sensitivity, Broman-Fulks[167] reported a .61 SD difference between exercisers and controls. We also re-examined data from a subset of highly anxious patients ( $STAI \geq 45$ ;  $N=32$ ) participating in our recently completed UPBEAT study[49] and found an effect size of .85 SDs on the STAI for both active treatments vs. placebo controls. We note that our power estimates are conservative in that the R-squared for the model is likely to be greater than .20 and dropout may be lower than 15%. With respect to the secondary outcome of HRV, our prior work showed that the R-squared between the baseline covariates and HRV was .73, greatly increasing the power of the tests of treatment on HRV. For the test of exercise vs. escitalopram on HRV, our primary CHD biomarker of interest, we will have a power of .80 to detect a .25 SD effect at alpha of .05. Finally, for our ancillary outcomes, including FMD, lipids, urinary catecholamines, and inflammatory markers, we have sufficient pilot data for FMD, which we use as an exemplar for power estimates: our earlier work showed that for FMD, the multiple R-squared between the baseline covariates (age, gender, ethnicity, and baseline FMD) and FMD was .50. Thus, we will have a power of .80 to detect a .34 SD effect for FMD with an alpha of .05. We estimate the power for the secondary analysis of treatment on time-to-clinical-event, assuming an event rate of 50% in the placebo group (based on unpublished data from our prior work[49]), 42 months for patient accrual, median follow-up time of 30 months and alpha = .05, is .80 to detect a reduction in event rate of 50% between both treatment groups and placebo, as well as .80 to detect a reduction in event rate of 56% between either intervention group individually and placebo. Unpublished data from our recently completed ENHANCED trial[168] revealed a 54% reduction in major adverse cardiac events among patients participating in CR compared to a matched control group of patients who did not participate in exercise-based CR.

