
**13. Data and Safety Monitoring:** Study participants will be closely monitored for side effects, level of anxiety, and suicide risk. All patients will receive a weekly phone call to assess their state of anxiety using the STAI-State instrument. For patients who have a secondary diagnosis of MDD, BDI-II item #9 will be administered along with the 20-item STAI; patients who score  $>1$  on the item #9 of the BDI-II or who are judged to be at increased risk for suicidality will be evaluated by our study psychiatrist and referred for further treatment. For patients with a secondary diagnosis of MDD, suicidality will be assessed at each visit and by interim telephone contacts as needed. Subjects may experience no response to treatment or a worsening of symptoms; however, all subjects will be carefully monitored and withdrawn from the study if their symptoms worsen. If patients become suicidal, they will be evaluated by the treating psychiatrist

and appropriate referral or admission procedures will be initiated, such as to their referring physician or to the Duke Outpatient Affective Disorders Program, the Duke Psychology Clinic, or a local mental health center. Our study coordinator will contact the patient within 24 hours to make sure that he or she followed through with the referral. Furthermore, at the conclusion of the interventions, patients will be followed bimonthly via telephone and referred to their local physicians for further treatment, if necessary, or to the Outpatient Treatment Program at Duke University Medical Center or to the Duke Psychology Clinic.

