**Management of Worsening Depression or Active Suicidal Ideation:** In addition to weekly assessments, participants are advised to contact the study team should they believe their symptoms become worse or they develop active suicidal ideation. An interim visit or phone contact with [name] may be required. Patients who report suicidal ideation will be immediately evaluated by [name], the study psychiatrist. Patients who present with acute and active suicidal ideation will be terminated from the study and referred for further psychiatric care as needed.

**14. Privacy, Data Storage, and Confidentiality:** All participant data will be kept in locked offices and electronic data in password-protected folders on the shared drive that are only accessible to key personnel.

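### The clinical-event count model names no follow-up time, and the protocol does not settle whether patients removed from the study stay in event follow-up

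*Combined protocol and SAP*

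**What the plan says.** Section 12, Data Analytic Approach, describes the event analysis in one sentence: "we will compare the treatments on the number of clinical events using a generalized linear model with the appropriate distributional form", giving negative binomial as an example, and "using the same contrasts and covariates as in the linear model described above". That linear model has "ethnicity, age, gender, and pre-treatment measure of the outcome variable as the adjustment covariables". No offset, exposure time or rate is mentioned. The same section applies intention to treat in all models and handles missing data by full information maximum likelihood.

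Follow-up will vary. The Power Analysis assumes "42 months for patient accrual, median follow-up time of 30 months", and it powers the outcome as time-to-event, a form of analysis that the Data Analytic Approach does not describe. Section 4.V collects hospitalisations, "emergency room visits, revascularizations, and any deaths for up to 4 years post-treatment". Section 4.VI says that events come from review of medical records.

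Three statements bear on who stays in follow-up:

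- Section 13, on worsening symptoms: "all subjects will be carefully monitored and withdrawn from the study if their symptoms worsen".
- Section 13, on suicidal ideation: "Patients who present with acute and active suicidal ideation will be terminated from the study".
- Section 12, on dropouts and non-completers: "Participants who voluntarily drop out of treatment or who are unable to complete our protocol will not be replaced but will undergo follow-up assessment".

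**The concern.** A count is comparable between arms only if the arms were observed for comparable time. Under the stated model, a patient whose records are last reviewed at week 5 enters as zero events, with the same standing as a patient who was event-free for four years. Intention to treat and maximum likelihood do not repair this, because a shortened count is an observed value and not a missing one.

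Whether such patients will exist depends on how the three statements are read together. Section 13 speaks of leaving the study, not of leaving treatment. Section 12 promises follow-up to people who stop or cannot complete, but does not say whether a patient removed by the investigator is among them. If event collection ended for removed patients, and more were removed from one arm, that arm would appear to have fewer events. At stake are the event ratio and its test. The placebo arm has only 30 patients, so a 10-point difference there is three people.

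**Working it through.** **The plan's own figure.** The only figure for this outcome is the stated power of .80, for a 50% reduction (both active arms against placebo) and for a 56% reduction (one active arm against placebo). It was not reproduced. Two-sided with 150 patients, the both-arms comparison gives .75 (proportions .50 against .25), .50 (hazard ratio .5, 50% cumulative) or .77 (50% per year for 2.5 years). The one-arm comparison gives .77, .57 or .83. No single reading gives .80 within two points for both. That is a separate matter, and nothing below depends on it.

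**Spread of follow-up.** If accrual is even over 42 months and there is one closing date, a 30-month median implies 30 ± 21, or 9 to 51 months. Entry date is independent of arm, so mean follow-up is 30 months in both and the expected count ratio is unaffected.

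**Effect of early loss.** Inputs from the plan are 30 months of mean follow-up if retained and removal within the 3-month treatment period. Assumed are 1.5 months contributed by each removed patient, a proportion lost *l* in each arm, and event risk unrelated to loss. Mean follow-up is

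*m* = (1 − *l*) × 30 + *l* × 1.5

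This gives 28.575 months at 5% loss, 25.725 at 15% and 21.45 at 30%. With a true rate ratio of 1, the expected active/placebo count ratio is the ratio of the two means:

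| Lost, active | Lost, placebo | Calculation | Count ratio |
|---|---|---|---|
| 15% | 15% | 25.725 / 25.725 | 1.00 |
| 5% | 15% | 28.575 / 25.725 | 1.11 |
| 15% | 5% | 25.725 / 28.575 | 0.90 |
| 0% | 15% | 30 / 25.725 | 1.17 |
| 15% | 0% | 25.725 / 30 | 0.86 |
| 5% | 30% | 28.575 / 21.45 | 1.33 |

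If removed patients contribute 3 months, the second, third and last rows become 1.10, 0.91 and 1.31. With a true ratio of .50 and losses of 8% active and 15% placebo, *m* in the active arms is 27.6 + 0.12 = 27.72, and the expected ratio is .50 × 27.72 / 25.725 = .54.

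**Simulation.** Negative binomial counts were simulated for 120 active and 30 placebo patients, with 30% annual risk (Section 4.VI), 9 to 51 months of follow-up and dispersion .5 (assumed).

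- True ratio .50, losses 8% active and 15% placebo: .54 and power .51 without follow-up time; .50 and power .62 with a log follow-up offset.
- True ratio 1: 1.15 (5% active, 15% placebo), 0.90 (15%, 5%), and 1.31 with type I error .12 (5%, 30%).
- Staggered entry with no loss: no bias, and power .63 without the offset against .64 with it.
- Equal 15% loss with a true ratio of .50: no bias, but power fell from .61 to .52 in a similar run.

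**Limit of the offset.** Suppose 15% of each arm has twice the event rate of the rest (Section 3 reports roughly 2-fold risks with anxiety), the true ratio is 1, and all of these patients are lost on placebo but only a third of them (5% of the arm) on active treatment. In units of the ordinary patient's monthly rate:

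- Placebo: events 25.5 + 0.15 × 1.5 × 2 = 25.95; time 25.725; rate 1.009.
- Active: events 25.5 + 0.10 × 30 × 2 + 0.05 × 1.5 × 2 = 31.65; time 28.575; rate 1.108.

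The raw-count ratio is 31.65 / 25.95 = 1.22. Dividing by time lowers it to 1.108 / 1.009 = 1.10, not to 1. With event collection continued for everyone, the ratio is 1.00 with or without an offset.

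**The case against.** The best reply is that the documents lean towards continued follow-up. A patient stopped by the investigator can fairly be called one who was unable to complete the protocol, and Section 12 gives such patients follow-up assessment. Intention to treat covers all models. Record review does not require the patient to attend or to stay on treatment. Section 13 also refers to tracking all participants after the interventions. The event model is a one-sentence outline, and leaving an offset unnamed does not exclude one. The Power Analysis names a time-to-event analysis, which would handle unequal follow-up.

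Most of this stands. A reader might infer that removed patients do leave event follow-up, that placebo will lose more of them because removal follows worsening, and that the event ratio will therefore be pulled towards or past 1. The documents do not support that chain. Section 13 does not say that event collection ends. The 15% attrition is not split by arm or cause. Section 10 expects up to 10% dropout from drug side effects, which could place the greater loss on active treatment. A reader might also take the post-treatment dating in Section 4.V to exclude events during the intervention. It reads more naturally as a time horizon, though it does leave the starting point unstated.

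The reply does not remove two gaps. The sections can be read in opposite ways on who remains in event follow-up. And the count model and the time-to-event power statement describe two different analyses, of which only the first is given terms, without follow-up time.

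**Conclusion.** The concern holds as a gap in specification with a conditional bias. The event model should carry follow-up time, and the plan should state that event collection continues for removed patients. Bias needs both lost event data and loss that differs by arm; neither is established, and the direction is open. If both occur, the shift is about 10% in the ratio for a 10-point difference in early loss. The 5%/30% case, with type I error near .12, is extreme and serves as an outer bound. These sizes rest on assumed removal rates, removal times and dispersion. The Power Analysis calls the event comparison secondary and Section 2 lists medical events among matters to explore, so the HADS-A conclusion is untouched. The correction is still worth making, because event data not collected may be hard to recover later.

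**What to change.** 1. Reconcile the non-completer statement in Section 12 with the two removal statements in Section 13, so that the record-based event collection of Section 4.VI covers every randomised patient unless consent for it is withdrawn. This concerns data collection only; the clinical withdrawal rules need not change, and no view is taken on them. It is the main safeguard, since an offset alone removes the bias only if loss is unrelated to event risk.
2. In Section 4.V, state that events are counted from randomisation.
3. In Section 12, either add log(time from randomisation to last record review, death or withdrawal of consent) as an offset in the count model, or specify the time-to-event analysis that the Power Analysis already names. State which one is the event analysis.

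The cost is a few sentences, one model term and a little more record review. No extra visits are needed.

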## **9. Study Interventions:**

**Randomization:** All eligible subjects will be randomly assigned to one of the 3 treatment conditions. Randomization will occur after each subject has completed the assessment protocol and will adhere to standard procedures for randomized clinical trials.[162] We will employ a conditional randomization procedure wherein equal proportion of participants with anxiety disorders will be assigned to the respective treatment groups. We also will stratify by gender (male/female), history of myocardial infarction (yes/no), and age (<60/≥60). Our anticipated sample size is 150 patients, wherein randomization will include 60 patients to Exercise Training, 60 patients to Medication, and 30 patients to Placebo. We anticipate needing to consent 300 patients in order to reach our sample size goal.

**1. Supervised aerobic exercise.** Patients will exercise three times per week, under medical supervision, at a level of 70-85% of their  $VO_{2peak}$  as determined at the time of their baseline exercise treadmill test. Patients' exercise will consist of 10 minutes of gradual warm-up exercises followed by 35 minutes of continuous walking, biking, or jogging, and 5 minutes of cool down exercises for a total a 50 minutes per session. Patients will be instructed to monitor their radial pulses and will be checked at least three times per session to ensure that they are within their prescribed exercise training ranges. Weekly supervised exercise sessions may take place at one of four sites chosen by the patient: Duke Cardiopulmonary Rehabilitation at Croasdaile, WakeMed Health and Hospitals, UNC Wellness Center at Meadowmont, and Alamance Regional Medical Center. Although depending on the geographic location of participants, other sites may be recruited for participation.

At UNC Wellness Center at Meadowmont, [name] will oversee recruitment and exercise interventions, provide active consultation and collaboration in all aspects of the study, and contribute to data analysis and manuscript writing, while [name] will assist with recruitment and oversee participation of subjects. Both investigators will have access to Duke PHI. At WakeMed, [name] and staff will work in their normal capacity to supervise patient exercise. At Alamance Regional Hospital, now owned by Cone Health, [name] will work in her normal capacity to supervise patient exercise.

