We also will examine treatment effects for a number of additional supportive outcome measures (e.g., BDI-II, QoL, inflammatory markers, BRS, urinary catecholamines, etc.). Significant treatment effects for these variables will help us interpret our primary outcomes and may inform further study and clinical application. For example, if the additional quality of life variables or CHD biomarker measures are also responsive to exercise treatment, it may indicate that exercise has a more global salutary effect above and beyond reducing anxiety. Despite their importance, we recognize that conducting these additional comparisons raises the potential for an inflated Type I error rate. We will therefore note in publications that these additional analyses represent exploratory analyses. We shall otherwise carry these analyses out using the same modeling approach as we do for the primary treatment analyses, attending in particular to the distribution of the residuals for each model and modifying our approach accordingly. The above models can be easily extended to include the 6-month follow-up measurement occasion.

Prior to conducting these analyses, preliminary examination of the assumptions of the model will be conducted to examine the homogeneity of regression assumption. This assumption requires that the relationship between treatment and the response variable be homogeneous for each level of the adjustment covariables. Should the data indicate that this assumption is violated, we will model the corresponding multiplicative (interaction) term(s). In addition to assessing the adequacy of the model with respect to the homogeneity of slopes assumption, we also will evaluate the model for violations of heteroscedasticity of errors and non-linearity using standard graphical methods. Should these assumptions be violated, appropriate transformations (e.g., Box-Cox method) will be made. All analyses of treatment effects for secondary hypotheses concerning continuous or binary variables will be conducted using the modeling capabilities available in MPlus.

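### The primary HADS-A model may change after assumption checks, with no rule for which treatment effect is then reported

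*Combined protocol and SAP*

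**What the plan says.** Section 12, Data Analytic Approach, sets out the primary analysis. Post-treatment HADS-A is regressed on two planned contrasts (both active arms against placebo; exercise against escitalopram), adjusting for ethnicity, gender, age and baseline HADS-A. No overall test comes first: "The contrast tests among treatment groups will be examined directly". The Power Analysis paragraph assumes the same model, with "an alpha of .05, a linear model with age, gender, ethnicity, and baseline HADS-A score as covariates", and names active treatment against placebo as the comparison of main interest.

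Two paragraphs after the model is set out, the plan describes checks to be made before analysis. On equality of slopes it says: "Should the data indicate that this assumption is violated, we will model the corresponding multiplicative (interaction) term(s". On unequal variances and non-linearity, judged from graphs, "appropriate transformations (e.g., Box-Cox method) will be made". Both are worded as things that will be done to the model, not as supplementary analyses.

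The plan does not state which test of slopes is used, at what level, or how many terms are tested. Nor does it state how covariates are centred, which treatment effect is reported once an interaction is in the model, or whether the unmodified model is still reported. Elsewhere the same section is more careful. Moderators are exploratory and screened by a pooled test, and adjustment for medication change is labelled a sensitivity analysis.

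**The concern.** Once a treatment-by-covariate product enters, the contrast coefficient is no longer the average effect. It is the effect at covariate value zero. With uncentred age or baseline HADS-A, that means a patient aged 0 or with no anxiety. Section 5 admits patients aged 40 or more with HADS-A of 8 or more; the opening of Section 4 gives 11 or more, and zero is outside both. A transformed outcome likewise no longer matches the HADS-A difference on which the trial was powered.

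In a randomised comparison, the covariate-adjusted contrast estimates an average effect whether or not slopes are equal. The check therefore protects nothing that the primary test needs. What is at stake is that the single test on which the trial is judged may differ from the one specified, with an error rate set by details that the plan leaves open.

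**Working it through.** **1. The plan's own figure.** The plan gives no error rate for the check-then-fit procedure, only alpha .05. Its one quantitative statement about the primary model is power: "We estimate that a sample size of 150 (127 after attrition) will yield .80 power to detect at least a .45 SD difference". Inputs are "a conservative estimate of the R-squared of .20 for the full model predicting post-treatment HADS-A", loss of 15% of patients, and allocation of "60 patients to Exercise Training, 60 patients to Medication, and 30 patients to Placebo"; sidedness is not stated, so two-sided is assumed.

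- Residual SD = √(1 − .20) = .894. Split of 127 at 2:2:1: 25.4 placebo, 101.6 active.
- SE = .894 × √(1/25.4 + 1/101.6) = .1984.
- Power = Φ(.45/.1984 − 1.96) = Φ(.31) = .62, not .80. A 1:1 split of the 127 would give .81.

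That mismatch is a separate matter. It concerns the fixed model, and nothing below depends on it.

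**2. How often a false interaction enters.** Two contrasts by four covariates (ethnicity taken as two levels) give eight possible terms. Treating tests as independent, P(at least one) = 1 − (1 − a)^k.

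- Eight tests at .05, either contrast affected: 1 − .95^8 = .337 (simulated .33).
- The four terms that involve active against placebo: 1 − .95^4 = .185 (simulated .18).

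Only the second event changes the meaning of the primary contrast.

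**3. Simulation under no treatment effect and no interaction.** Arms of 25 placebo, 51 and 51; R-squared .20; 5,000 to 10,000 trials per setting; Monte Carlo SE about .002 to .005. Assumed, because the plan does not give them: ages around 64 (SD 9), 50% women and 25% minority as achieved proportions, and baseline HADS-A from 8 to 21. Each trial fitted the stated ANCOVA, tested interactions, refitted with those selected, and tested active against placebo.

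| Rule for adding terms | Any term added: formula (simulated) | Type I error, uncentred | Type I error, centred |
|---|---|---|---|
| None (fixed model) | 0 | .046–.055 | same |
| Eight tests at .05 | .337 (.33) | .14 | .050–.060 |
| Four 2-df tests at .05 | .185 (.18) | .105 | .052 |
| One 8-df test at .05 | .05 (.056) | .056 | .052 |
| Eight tests at .01 | .077 (.076) | .072 | .050 |
| Eight tests at .10 | .570 (.56) | .152 | .056 |

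For eight tests at .05, the uncentred figure was .143 with no attrition (N = 150) and .154 with R-squared .50. With only the 0/1 covariates left uncentred it was .069. A second simulation with the same allocation and R-squared gave .053 fixed, .149 uncentred and .057 centred, with a term for the primary contrast entering in .19 of trials.

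**4. Why coding matters.** For a covariate with mean m and SD s, the coefficient at zero has a standard error about √(1 + (m/s)²) times that at the mean. With age 64 and SD 9, m/s = 7.1 and the ratio is √(1 + 7.1²) = 7.2. The correlation of that coefficient with the interaction estimate is about −7.1/7.2 = −.99. A chance interaction therefore makes the coefficient at zero look significant too; centring removes the link.

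The arithmetic closes in one run. A term was selected in .335 of trials, where the uncentred test rejected in .317; elsewhere it rejected in .052. So .335 × .317 + .665 × .052 = .106 + .035 = .141.

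**5. Transformation.** Box-Cox on a rounded HADS-like score plus 1, with the power chosen by likelihood, gave type I error of .046 to .051. There was no inflation in these settings, which used normal errors.

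**The case against.** **Scope.** The assumptions paragraph follows one on supportive outcomes and ends with a sentence on secondary hypotheses, so its checks might be meant only for those. This stands as an ambiguity. The paragraph does, however, use the terms of the primary model, the supportive outcomes are said to follow the primary modelling approach, and nothing exempts HADS-A. Covering the primary model is the natural reading, but it is not explicit.

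**The rates rest on an assumed rule.** A reader might infer that one trial in three has its primary contrast altered. The documents do not support that. They specify no eight-test rule, and one in three counts changes to either contrast. The only interaction screen the plan describes, for moderators, is pooled. It does not bind the assumption checks, but one pooled 8-df test would bring the rate to about .05.

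**The error rate depends on coding.** A reader might also infer that the plan carries a type I error of .14. It does so only if covariates are uncentred and the effect is read at zero, which the plan nowhere says will happen. Nor is .14 a ceiling, since tests at .10 gave .152. Silence on coding is also no evidence that coding would be chosen after seeing results.

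**Transformation.** It is tempting to say that the transformation rule inflates error in the same way. That was not shown. Box-Cox being undefined at a score of 0 is minor: it is named only as an example, and adding a constant avoids the problem.

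What survives is that the plan commits to changing the model on the data without saying when, how, or which effect is then reported.

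**Conclusion.** The concern holds as a specification fault with conditional consequences. Assuming eight separate tests at .05, a false interaction alters the active-versus-placebo contrast in about one trial in five, and either contrast in about one in three. Across other plausible rules, the chance that any term enters runs from about .05 to .57. Type I error of the primary contrast runs from about .05–.06 (centred covariates, or a single pooled test) to about .14–.15 (uncentred covariates, effect read at zero), against about .05 if the model stays fixed. The pre-test thus gains nothing when coded well and distorts the primary test when coded badly. For transformation, the objection is the change of scale and not the error rate.

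These figures rest on the assumed covariate distributions, two-sided testing, and the reading that the checks reach the HADS-A model. Confidence is moderate. The change should be made, but the fault does not by itself invalidate the design.

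**What to change.** In the assumptions paragraph of Section 12, state that the main-effects ANCOVA on untransformed HADS-A, as set out under Data Analytic Approach, is the primary analysis whatever the checks show. Use robust standard errors (for example MLR in Mplus) to handle unequal variances. Report treatment-by-covariate models, with centred covariates, and transformed-outcome models only as sensitivity or exploratory analyses, alongside the moderator analyses already planned. Robust errors do not address non-linearity, so a concern of that kind belongs among the sensitivity models.

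The cost is two or three sentences and a little extra analysis, with no effect on patients or data collection. The downside is a possible small loss of efficiency if residuals are markedly non-normal.
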